To feedback on the progress being made to improve secondary care outcomes for patients referred to the ICTs in NEHF, introduced in July 2015 in each of the five localities of NEHF Clinical Commissioning Group (CCG) ('the intervention').

What the study will look at

The study will examine whether there is an impact on secondary care outcomes ('endpoints') for patients who were referred to ICTs (the 'intervention group') between July 2015 and June 2017.

The IAU will compare these outcomes with those of other patients who were also registered in a GP practice in the NEHF CCG and who were similar (e.g. in age, gender, comorbidities, number of hospital admissions in the year prior to the referral to the ICTs). This 'local matched control group' will have had access to all the same services within the CCG, apart from the ICTs. As the range of primary and acute care systems (PACS) services differed slightly across the five localities, the IAU will select controls from within the same locality as the ICT patients.

The primary outcomes examined will be:

- number of emergency admissions
- number of emergency admissions for long-term ambulatory care sensitive (ACS) conditions
- number of emergency admissions for urgent care sensitive conditions
- number of A&E attendances

- average length of stay following an emergency admission.

The secondary outcomes examined will be:

- number of emergency readmissions within 30 days of discharge
- number of elective admissions
- number of outpatient attendances
- average length of stay following an elective admission
- number of emergency bed days
- number of elective bed days
- the proportion of deaths outside of hospital (used as a proxy for end-of-life care occurring in the patient's place of choice).

Outcomes in the intervention group will be compared with those of the local matched control group over a period of up to 23 months, taking into account each person's length of time in the study.

If the sample size is large enough, further analyses will look separately at each of the five localities to estimate the impact of the ICTs in each setting. In addition, data permitting, the study will investigate the impact of ICTs on the subgroup of patients who suffer from mental ill health, since mental health professionals were core members of the ICTs.

Data the IAU will use

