Often a referral will be preceded by a discussion between the GP or another health professional and the patient. Therefore, the referred patient group is likely to only contain those patients who agreed to being referred to an ICT. However, anecdotally, occasionally a referred patient, for example from social services, refuses to accept a service suggested by the ICT. The IAU does not have access to these data.

Moving forwards, it is intended that the ICT model will not purely be responsive to need, but also include proactive case finding and management to target people who have the potential to become high service users in the absence of proactive management and support.¹⁴ It plans to use more systematic criteria for selection, including the use of the ACG risk stratification tool.¹³ Farnham started in April 2017 to pilot various criteria to identify complex patients who require integrated case management. NEHF CCG is currently investigating using the following threshold criteria to proactively identify patients who may benefit from ICTs, in addition to the risk stratification tool:

- multi-morbidity: patients who have four or more chronic conditions
- complex multi-morbidity: patients who have three or more chronic conditions affecting three or more body systems
- poly-pharmacy: patients prescribed 10 or more drugs
- housebound
- nursing home resident
- residential home resident.

Any one of these criteria would qualify a patient to enter an ICT register. A subset of these patients would then be selected for referral to the ICT, using the ACG tool to identify patients at rising risk of emergency hospital admission. However, for the study period of this evaluation, patients were mainly referred to ICTs based on clinical judgement, rather than through the application of formal criteria such as these.

Intended impact of ICTs on outcomes

The explicit aims of the ICTs are to:¹²

- reach the top 2% of patients at risk of emergency admission (either with crisis management, a proactive intervention to prevent crisis or supporting self-care/prevention)
- reduce A&E attendances
- reduce emergency admissions
- improve patient-reported outcome measures (PROM) scores, demonstrating a positive impact on ICT patients' health, health confidence, experience and wellbeing.

Other intended impacts of the ICTs are to reduce:¹²

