As recipient data controllers, NEHF CCG/NHS England can use their powers of disclosure under the Health and Social Care Act 2012 to share data to support IAU evaluations. To facilitate this, it may be necessary for the CCG local data to be transferred securely from the Data Services for Commissioners Regional Office (DSCRO) providing services to the CCG to NHS England's DSCRO (Arden and Great East Midlands) to enable it to be de-identified and linked to NHS England's national SUS data and/or other data as required to support the evaluation. The linked data will then be anonymised further (i.e. different pseudonyms applied) to mitigate the risk of re-identification when the data are made available to analysts in the IAU who will be undertaking the evaluation.ⁱⁱ

Study endpoints

Primary outcomes

The primary outcomes to be examined by the study are:

- number of **emergency admissions** per patient over the follow-up period
- number of **chronic ACS emergency admissions** per patient over the follow-up period
- number of **emergency admissions for urgent care sensitive conditions**
- the number of **A&E attendances** per patient over the follow-up period
- **average length of stay following an emergency admission** per patient.

All count endpoints will be modelled allowing for varying study lengths, by including an offset for amount of time at risk in the statistical analysis. The length of the follow-up period for each patient will vary between 1 and 23 months, depending on the date on which they entered the study (e.g. when during the study period they were referred to an ICT) and if they died or moved away during the study period (i.e. whether their time in the study was curtailed) (see section on Index dates and follow-up period, p. 23).

Emergency admissions are defined as separate hospital spells that either occur through the emergency room or as a result of direct, urgent referrals from a GP or other professional. Many emergency admissions are not avoidable with good care; therefore, evaluating ACS admissions may be a more appropriate outcome when evaluating a health care intervention.

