Appropriate baseline variables will be included in both the matching and the regression models. All baseline variables are calculated on pre-period data. Potential baseline variables to include in the matching or as covariates in the modelling are listed in Table 3.

Table 3. Potential baseline variables

Category	Variables at patient level
Demographics & socio-demographics	
 • Approximate age at index date • Gender • Ethnicity • Average socioeconomic deprivation deciles, based on the Index of Multiple Deprivation (IMD) 2015, available at layer super output area (LSOA) level • Urban/rural classification at lower LSOA level, based on the 2011 census
Prior hospital use	
 • Number of emergency admissions in the last 60 days of the pre-period • Number of emergency admissions in year -1, the last year of the pre-period (i.e. 365 to 1 day before index date) • Number of emergency admissions in year -2 of the pre-period (i.e. 730 to 366 days before index date) • Number of ACS emergency admissions in the last 60 days of the pre-period • Number of ACS emergency admissions in year -1 of the pre-period • Number of ACS admissions in the year -2 of the pre-period • Number of elective admissions in year -1 of the pre-period • Number of A&E attendances in year -1 of the pre-period • Number of outpatient attendances in year -1 of the pre-period • Number of missed outpatient visits in year -1 of the pre-period • Average length of stay in year -1 of the pre-period
Health variables	
 • Elixhauser list of comorbidities, identified in the pre-period • Specific comorbidities linked to frailty, identified in the pre-period³⁰ • Other comorbidities predictive of hospital emergency admission, as identified in the Inpatient Outpatient A&E and GP(IPOPAEGP) model,³¹ identified in the pre-period

	
 • Number of Elixhauser comorbidities in the pre-period • Number of frailty comorbidities in the pre-period
Support	
 • Resident in a nursing or residential home
Time period	
 • Index date/period (quarter & year, e.g. q1y1, q2y1...)
Level of care available	
 • Locality in which the patient is registered with a GP

All comorbidities will be defined using data from any diagnosis field in any hospital admission in the pre-period.

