Modelling options also included adjusting for only a list of 'core' variables and those variables considered most predictive of the outcome, as the low number of events for some of the outcomes may otherwise have led to over-parametrised models. The most predictive variables were identified by running a lasso regression and where possible included all core variables as a minimum.⁵⁷ Variables considered 'core' were: age; gender (male or not male); IMD quintile; locality; Charlson Index; number of Elixhauser comorbidities; number of frailty comorbidities; history of mental ill health; index date quarter; hospital use in year prior to index date; and emergency admissions, CACS emergency admissions and UCS emergency admissions in the two months prior to index date.

Due to low numbers of care home residents (<10) in both ICT and matched control groups, analyses only adjusted for whether patients lived at home or in a care home (i.e. no differentiation between nursing and residential homes).

Following the analysis, it was found that outpatient appointments included community data from Virgin Care Services that had been uploaded to SUS in error. These appointments were removed from the data and the analysis of outpatient hospital use was redone. Other outcomes were not reanalysed; therefore in the case where these analyses adjusted for outpatient appointments in the year prior to the study, this variable would have contained some community outpatient appointments from Virgin Care Services.

Modelling options did not include multilevel models with locality as a random effect, as five localities were considered too few groups to adequately run such a multilevel model.

Acknowledgements

We are grateful to the North East Hampshire and Farnham CCG team for their support and their review and feedback on an earlier version of this statistical analysis protocol. We are also grateful to [name] and [name] for their peer review comments on an earlier version.

References

- ¹ NEHF CCG. Happy, Healthy, at Home (accessed 29 June 2017). Available from: www.northeasthampshireandfarnhamccg.nhs.uk/about-the-ccg/happy-healthy-at-home
- ² Moran P. Short Stay Emergency Admissions. NEHF CCG, available on request. 2016.

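### A&E attendances, a primary outcome, have no 60-day baseline count, so a rise in A&E use just before referral may leave some confounding that the balance check would not show

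*Protocol*

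**What the plan says.** The Summary lists "number of A&E attendances" among the primary outcomes. Study endpoints, Primary outcomes, defines it as "A&E attendances per patient over the follow-up period". Intended impact of ICTs on outcomes includes, as an explicit aim, to "reduce A&E attendances".

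Table 3 (Section 2, Baseline variables, Prior hospital use) gives emergency admissions three look-back windows. The shortest is "Number of emergency admissions in the last 60 days of the pre-period". The other two are yearly counts: year -1, which ends the day before index and reaches back 365 days, and year -2, which covers the twelve months before that.

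ACS admissions have the same three windows. A&E attendances have one: "Number of A&E attendances in year -1 of the pre-period".

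The addendum (Section 5, Statistical analysis) names a core set of adjustment variables. It includes hospital use in the year before index, and its only short-window items are "emergency admissions, CACS emergency admissions and UCS emergency admissions in the two months prior to index date". None of these is an A&E count.

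Three other passages bear on the point. Pre-period argues that capturing hospital activity shortly before referral, in both matching and regression, outweighs the risk that other services have altered that activity. Choice of matching variables ranks candidates by how well they predict emergency admissions. Diagnostics assesses balance over the variables listed under Baseline variables.

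**The concern.** Referral in the study period was mainly by clinical judgement, and the protocol says it cannot identify which characteristics drove it. A cluster of recent A&E visits is a plausible prompt. If it is one, an ICT patient whose visits fell mostly in the last two months can be matched to a control whose equal number of visits was spread over the year. If the recent rise continues after index, the control has the lower expected rate, and the ICT group shows more A&E attendances with no effect of the ICTs.

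The plan's safeguards do not look there. The balance table covers only listed variables. The lasso in the addendum can select only from variables that were derived. The check for unobserved confounding uses mortality, which need not respond to a run of visits that ended in discharge. The protocol also says that its confidence intervals do not reflect unobserved confounding.

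**Working it through.** The protocol states no bias, power or sample size figure on this point, so there is nothing to reproduce.

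**Step 1. Count the windows.** Emergency admissions 3, ACS admissions 3, A&E attendances 1.

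**Step 2. What the year -1 count contains.** Year -1 runs from 365 days to 1 day before index. The last 60 days lie inside it, so recent attendances are counted, admitted or not. What is lost is their timing.

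**Step 3. How far a recent rise is diluted.** Let a patient's yearly rate be r, rising s-fold in the last 60 days. The expected year -1 count is r × (305 + 60s)/365.

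- s = 2: r × 425/365 = 1.16r, while the current rate is 2r.
- s = 4: r × 545/365 = 1.49r, while the current rate is 4r.

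**Step 4. Effect on the rate ratio with no ICT effect.** None of these assumptions comes from the protocol: gamma-distributed A&E rates with mean 0.5 or 1.0 a year; no rise, or 10% of patients with a 2- or 4-fold recent rise that persists into follow-up; odds of referral multiplied by 2 or 5 after any attendance in the last 60 days. Within exact strata k of the baseline count, the ratio is the sum of expected ICT-group events over the sum of n(ICT, k) × mean control rate in k.

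| Mean rate | Rise | Referral odds | No matching | Year -1 A&E only | Year -1 plus 60-day A&E |
|---|---|---|---|---|---|
| 0.5 | 2-fold | ×2 | 1.077 | 1.008 | 1.002 |
| 0.5 | 2-fold | ×5 | 1.248 | 1.020 | 1.001 |
| 0.5 | 4-fold | ×2 | 1.132 | 1.039 | 1.007 |
| 0.5 | 4-fold | ×5 | 1.412 | 1.100 | 1.003 |
| 1.0 | 2-fold | ×2 | 1.130 | 1.008 | 1.000 |
| 1.0 | 2-fold | ×5 | 1.353 | 1.020 | 1.001 |
| 1.0 | 4-fold | ×2 | 1.188 | 1.042 | 1.003 |
| 1.0 | 4-fold | ×5 | 1.499 | 1.085 | 1.001 |

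With no rise, the year -1 count alone gives 0.997 to 1.003, which is 1 within simulation noise.

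**Step 5. Add the plan's admission counts.** With 45% of attendances assumed to be admitted, and stratifying also on 60-day, rest-of-year -1 and year -2 admissions, the residual is about 1.00 to 1.01 for a 2-fold rise and about 1.02 to 1.05 for a 4-fold rise. This is roughly half the year -1-only residual. The halving depends on any attendance prompting referral. In a check where only visits ending in discharge did so, the admission counts removed little, and the residual stayed close to the year -1-only column.

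**Step 6. Scale against sampling error.** With 900 per group (the protocol's expected number) and an assumed mean of 1 and variance of 2 attendances per patient, SE(log ratio) = √(2 × 2/(900 × 1²)) = 0.067. By comparison, ln 1.05 = 0.049 and ln 1.10 = 0.095.

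**The case against.** The strongest reply is that the plan already controls most of this. The year -1 count includes every recent attendance. Emergency admissions include those that come through A&E, so their 60-day count picks up part of a surge. Age, comorbidity, frailty and outpatient history, which the simulations leave out, may absorb more. The protocol nowhere says that A&E visits prompted referral; most referrers were GPs, with others from community and social care. Table 3 is a list of potential variables, and Statistical analysis allows other predictive covariates. The likely residual is also smaller than one standard error.

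Most of this stands, and it limits the size of the point. It does not remove it. Neither Table 3 nor the addendum names a recent A&E count, so the permission to add covariates was not used for this one. A bias below one standard error still shifts the estimate, and the interval does not show it.

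A reader might infer more than the protocol supports:

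- That recent A&E use without admission is wholly uncontrolled. It is not: it sits in the year -1 count.
- That the A&E result is biased by a known amount. A simulation with stronger referral dependence gave ratios of 1.04 to 1.13, but it used few of the plan's covariates and 12 replicates per scenario, with no Monte Carlo error reported. It does not describe this plan.
- That a year -2 A&E count is equally needed. In the table a 60-day count alone brings the ratio to 1.00 or 1.01, and no calculation isolates a benefit from year -2.

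**Conclusion.** The asymmetry is real and runs against the plan's own argument for using activity just before referral. The consequence is a possible residual confounding of one primary outcome, not a demonstrated bias. If a recent rise in A&E use both drives referral and persists, the spurious rate ratio is roughly 1.00 to 1.05 with the plan's admission counts included. It goes up to about 1.10 on the year -1 A&E count alone, and lies nearer that end if only discharged visits prompt referral. Without that dependence it is about nil. The upward direction, against the ICTs, also needs persistence: a rise that subsided at once would not push the ratio up. These conditions are assumptions that the protocol neither states nor excludes. The change is worth making because it is cheap and tests the outcome's own recent history directly.

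**What to change.** Add the number of A&E attendances in the last 60 days of the pre-period to Table 3, the matching candidates, the balance table and the addendum's core list. Report its standardised difference in the matched groups against the plan's 10% mark, and rerun the A&E outcome adjusted for it. As the addendum shows the analysis has already been done, label the rerun as added afterwards and present it beside the existing estimate. A year -2 A&E count is optional.

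The cost is one derived variable, one more covariate and a rerun of one outcome. The 60-day window lies inside the year -1 window for which SUS A&E data are already used, so no new data are needed. The addendum records that the outpatient outcome was rerun after a data error, so a single-outcome rerun is practicable. Repeating the match itself would touch every outcome and need be considered only if the new standardised difference is not negligible.

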Length of stay following an emergency admission is defined as the number of nights spent in hospital, calculated as the difference in days between the date of discharge and the date of admission. An admission and discharge within the same day will result in a length of stay of zero days.²³ Average length of stay per person is calculated by adding a patient's emergency admission lengths of stay and dividing by the number of emergency admissions. Average length of stay was chosen as a primary endpoint over the related measure – the total number of hospital bed days. Although hospital bed days is one of the 'core metrics' used within NHS England for the New Care Models programme,²⁴ it may not adequately measure the effect of the ICTs, as this endpoint reflects the length of stay in hospital as well as the number of emergency admissions. The ICTs are trying to proactively identify patients, which may inflate the number of emergency admissions in the short term. These admissions are expected to be of shorter duration than if they had not been proactively identified. If the 'counterfactual', longer hospital stay in the control group only occurs after the end of the study period for some patients, the hospital bed days measure may not adequately reflect the changes, as no admission during the study period is equivalent to an admission with a zero length of stay. Hospital bed days are included as a secondary endpoint.

Secondary outcomes

Secondary outcomes, all calculated over the follow-up period, will be:

- number of emergency readmissions within 30 days of discharge, per patient
- number of elective admissions per patient

- number of outpatient appointments per patient (excluding 'did not attends', and defined using code Attended=5 or 6 in SUS)
- average length of stay following an elective admission per patient
- proportion of total emergency bed days per patient, relative to total number of days at risk (i.e. days in the follow-up period)
- proportion of total elective bed days per patient, relative to total number of days at risk (i.e. in the follow-up period)
- proportion of deaths outside of hospital (as proxy for dying in preferred place of death).

All count outcomes will be modelled allowing for varying study lengths, in the same way as for the primary outcomes described above.

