- 1.0 a table for showing study length and reasons for censoring (leaving the study).

Data cleaning and validation checks

Data cleaning and data validation checks will be performed by the IAU Data Management team, in accordance with the IAU Data Management Quality Assurance Process. Where appropriate, a summary of the results can be produced for the technical appendix.

Data flow diagrams

The following diagrams will be produced for the technical appendix:

- 1.0 data linkage process diagram
- 2.0 data flow diagram of study cohort selection.

5. Addendum

This section has been added to the original statistical analysis protocol (SAP) document to provide further clarifications and information on modifications to the original SAP. The original SAP was agreed in September 2017 with this section added in July 2018.

Definition of study cohort, page 18

In addition to the exclusion criteria described on page 18 of this document, the following exclusion criteria were applied prior to the analysis:

- Patients with no valid Lower Layer Super Output Area (LSOA) geographic area – this variable was used to determine a patient’s level of socioeconomic deprivation
- For potential control patients, patients more than 2 years’ older than the oldest ICT patient or more than 2 years’ younger than the youngest ICT patient – this was to limit the size of the dataset of potential controls in the matching process

Study endpoints, page 21

Here we provide further clarification on how variables were defined.

Elective admissions are defined as those that are ‘ordinary’ or day cases and exclude maternity and regular day/night cases.

When calculating readmission rates, the NHS Outcomes Framework guidance⁵⁶ was followed, with the exception of also including elective day cases as potential offsets for the calculations. This was consistent with the definition of elective admissions described above, which includes both ‘ordinary’ and day cases.

For the variable average length of stay in the year prior to the index date, any hospital spell that starts in the pre-period but continues into the follow-up period was included in its entirety within the pre-period. For the outcome measure average length of stay in the follow-up period, we only included spells that both start and finish within the follow-up period. There is no expected bias between the ICT and matched control groups, as both had access to the same hospitals.

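### Table 3 lists one prior-year average length of stay with no admission type, so it cannot be the baseline value of both the emergency (primary) and the elective (secondary) length-of-stay outcome

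*Protocol*

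**What the plan says.** Protocol, Study endpoints, makes "average length of stay following an emergency admission" a primary outcome. It is calculated per patient by "adding a patient's emergency admission lengths of stay and dividing by the number of emergency admissions", and a same-day stay scores zero nights. Average length of stay after an elective admission is a separate secondary outcome, calculated in a similar way.

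Table 3 (Baseline variables) labels its prior-year admission counts by type, for example "Number of elective admissions in year -1 of the pre-period". The only length-of-stay row is "Average length of stay in year -1 of the pre-period", with no type. Table 3 is a list of potential variables. The surrounding text expects all of them to enter the regressions, and the Statistical analysis section also allows other covariates that predict the outcome.

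The Addendum (Study endpoints, page 21) comments on the prior-year variable only for stays that cross the index date: "any hospital spell that starts in the pre-period but continues into the follow-up period was included in its entirety within the pre-period". It also states that elective admissions cover ordinary admissions and "day cases and exclude maternity and regular day/night cases". The Addendum's core adjustment set (Statistical analysis, page 30) names "hospital use in year prior to index date" without saying which measures that includes.

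**The concern.** For an outcome such as emergency length of stay, the natural covariate is the patient's own earlier value on the same measure. Here the outcomes are split by admission type and the baseline measure is not.

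If the baseline measure averages over all spells, elective stays change it without saying anything direct about emergency stays. Zero-night day cases pull it down and long elective stays push it up. The matched groups could then agree on every listed measure of prior use and still differ in prior emergency length of stay. Some precision could also be lost, in a study that warns that about 900 patients may be too few.

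**Working it through.** The plan states no power, variance or correlation for this outcome, so it has no figure of its own to reproduce. The check is a comparison of definitions, followed by illustrations on assumed inputs.

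**1. Which outcome has its own baseline value, under each reading of the row**

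| Spells in the Table 3 average | Emergency outcome (primary) | Elective outcome (secondary) |
|---|---|---|
| Emergency only | yes | no |
| Elective only | no | yes |
| All | no | no |

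No reading serves both outcomes. This conclusion does not depend on how the row is interpreted.

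**2. Equal counts, equal pooled average, different emergency stays** (all-spell reading)

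Pooled average = (emergency nights + elective nights) / (emergency spells + elective spells).

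- Patient A: one 14-night emergency stay and one day case. Pooled (14 + 0)/2 = 7; emergency 14/1 = 14.
- Patient B: one same-day emergency stay and one 14-night elective stay. Pooled (0 + 14)/2 = 7; emergency 0/1 = 0.

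Both have one emergency and one elective admission in year -1, so neither the counts nor the pooled average separates them. The point does not depend on day cases. Replace each zero-night stay by a one-night stay, and both pooled averages become (14 + 1)/2 = 7.5, with emergency values of 14 and 1.

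**3. Size, on assumed inputs**

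*Marginal correlation.* The first simulation used 200,000 patients per setting. It assumed 1 or 2 emergency admissions a year and 0.25 to 2 elective spells a year, 70% of them day cases. Emergency stays averaged 6 nights times a log-normal patient effect (SD 0.6 on the log scale).

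- The emergency-only and pooled averages correlated at 0.97 down to 0.84.
- Follow-up emergency length of stay correlated with the emergency-only baseline at 0.20 to 0.26, and with the pooled baseline at 0.19 to 0.26. The difference was below 0.01 in every setting.

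*Residual variance.* The second simulation used 400,000 people per setting. Stays were log-normal, with a person-level share of log variance of 0.3, 0.5 or 0.7. Emergency spells averaged 1.2 before and 1.0 after the index date, and day cases 0.5 to 2. The outcome was log(1 + mean emergency nights). The comparison model held the prior counts and the pooled average.

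- Adding the emergency-only average and an indicator for no emergency admission gave variance ratios of 0.95, 0.88 and 0.77, that is cuts of 5%, 12% and 23%.
- In a rebuild with similar inputs, the pooled average was first put on the log scale and the indicator added. The emergency-only value then gave a further ratio of only 0.99–1.00, 0.97–0.99 and 0.93–0.98.
- Added alone on the same raw scale, the emergency-only value cut residual variance by about 0 to 5%.

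Most of the 5 to 23% therefore comes from the log scale and the indicator. For a sense of scale, take 80% power as a reference point (the plan sets none). A 5% variance cut gives Φ((1.960 + 0.842)/√0.95 − 1.960) = Φ(0.915) ≈ 82%.

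**4. Why an indicator is needed**

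Entry requires only an emergency or elective admission within three years, so some patients will have no emergency admission in year -1 and their emergency average is 0/0. With Poisson admissions at an assumed 1 or 2 a year, that share is e⁻¹ ≈ 37% or e⁻² ≈ 14%.

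**The case against.** The strongest reply is that pooling is never stated. The Addendum's reference to any spell sits in a rule about stays that cross the index date. The next sentence refers to the follow-up outcome as average length of stay, also without a type, although that outcome is type-specific. A missing qualifier may be shorthand, and an emergency-only variable cannot be ruled out. A reader might infer that the plan adjusts for an average diluted by day cases and leaves the emergency value out of the model. The text does not support that as fact. The all-spell average is only the more natural reading, and Table 3 is a list of candidates. This reply stands, but it leaves the table in step 1 of the working untouched.

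A second reply is that the admission counts in the same table carry the missing information. If every elective stay has zero nights, emergency length of stay = pooled average × (emergency + elective spells)/emergency spells. The counts do separate a patient with one 14-night emergency stay and six day cases from one with seven 2-night emergency stays, although both average 2 nights. This stands in part. The identity fails once elective stays have nights: for Patient B it gives 7 × 2/1 = 14, and the true value is 0.

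The same counts answer another possible inference, that patients with no spell in year -1 would be confused with patients who had only same-day stays. The former have zero counts and the latter do not.

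Finally, a reader might expect a large gain in power. A baseline correlation of 0.5 would raise 80% to 90%, but only against a model with no baseline length of stay at all, which is not this plan. The simulations also leave out age, frailty and comorbidity, for which the plan intends to adjust, so the real gain may be smaller still.

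**Conclusion.** The point holds as a minor gap in definition. Two length-of-stay outcomes are type-specific, the single baseline row is not, and no emergency-only value is named for the primary outcome. That follows from the text on any reading. The possible hidden imbalance in step 2 of the working applies only if the row pools admission types.

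The gain in precision cannot be derived from the document. On assumed inputs it is small: about 0 to 5% of residual variance from the emergency-only value itself, and more when it is combined with the log scale and the indicator. Nothing in the protocol shows that the groups were in fact imbalanced on prior emergency length of stay, or that any estimate is biased.

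**What to change.** Replace the Table 3 row with two: prior-year average length of stay after emergency admissions, and the same after elective admissions. Put each on a log(1 + nights) scale with an indicator for no such admission in year -1. Check balance on both, and adjust each length-of-stay model for its own version. If the existing variable was already emergency-only, say so and add the elective one.

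Both variables come from SUS data already held. The cost is a revised table row, a short derivation, a refit of the two length-of-stay models and about three extra covariates. Those covariates matter mainly for sparse outcomes and small subgroups, given the Addendum's concern about over-parametrised models. The Addendum describes an analysis already run on about 750,000 potential-control records. A residual imbalance is therefore more cheaply handled by regression adjustment than by rerunning the matching, which would mean refitting every outcome.
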